12.0 Risks to Participants

12.1 Foreseeable Risks:

Questionnaires: Youth or parents may experience concerns when completing questionnaires dealing with symptoms of behavior problems. Any time one works with youth there is the possibility that they will reveal information about abuse and/or indicate that they are thinking of hurting themselves or others. We are mandated reporters, a fact that is revealed in

PROTOCOL TITLE: Does Social Buffering Continue to be Effective Over the Peripubertal Period
When Friends Share the Stressor Experience?

VERSION DATE: v.3.3 3.31.23

both consent and assent forms. However, in over a decade of working with children and youth drawn from our participant files, we have never encountered a reportable incident, so we consider this risk to be very low.

Trier Social Stress Test for Children. This is a social evaluative stressor. Public speaking evokes anxiety in many individuals. Also, the task involves deception, in that the judges do not render judgements as part of the task

The TSST activates stress-mediating systems because it serves as a threat to the social self. Public speaking produces anxiety in most people. However, answering questions in class, speaking in front of the class or school, and solving problems in front of teachers and classmates is a common occurrence in children's lives. Thus, the TSST standardizes a common everyday stressor. To reduce risk, youth are told that they can stop without prejudice if they choose.

Regarding deception: Because they are told they are being evaluated (and this is a necessary part of the procedure), after each TSST session, the youth will be debriefed to make it clear that there were no judgements made about the speech or math performed. It will be explained that performance in a social evaluation task was used in order to elicit a physical stress response. The youth will never receive any negative evaluations from adults as part of being in this study. Our previous experience with this deception and debrief is that youth tolerate the experience very well.

Saliva Sampling. We will collect saliva using passive drool, so this risk is eliminated.

12.2 Reproduction Risks: NA

12.3 Risks to Others: NA

13.0 Potential Benefits to Participants

13.1 Potential Benefits: The only direct benefit to participants is the small financial remuneration and the knowledge that they have contributed to a better understanding of human development among youth.

14.0 Statistical Considerations

14.1 Data Analysis Plan: 200 primary participants, including 100 females and 100 males. Within each group there will be 50 early and 50 late puberty participants.

Study Design. This randomized control study will assign study participants into one of four conditions: Close friend both tested, Unfamiliar Peer both tested, Received support from close friend who is not tested, and no partner. To perform the randomization, participants will first be placed into one of four groups based on sex and pubertal stage: early puberty, female;

PROTOCOL TITLE: Does Social Buffering Continue to be Effective Over the Peripubertal Period
When Friends Share the Stressor Experience?

VERSION DATE: v.3.3 3.31.23

late puberty, female; early puberty, male; and late puberty, male. Next, participants within a group will be randomly assigned to one of four conditions equally in order to have a balanced design. Pubertal stage will then be treated as a continuous variable.

Statistical Methods

Preliminary Analyses to Determine Covariates Need for Primary Analyses. The purpose of collecting data on potential covariates is to identify variables that are correlated with both the independent variable (social buffering condition, sex, pubertal stage) and the primary outcome measures. Those covariates that are associated with the independent and outcome variables will be controlled for in the primary analyses. Those that are not will be used to describe the sample, but will not need to be included in the analyses to obtain unbiased estimates. For each potential covariate (listed as “other type” in section 4.3, Outcome Variables), we will conduct correlations or t-tests with pubertal stage, and t-tests, ANOVAs, or chi-square tests (as appropriate) with sex and condition. If data do not confirm to modeling assumptions, we will use non-parametric analogs instead.

14.2 Power Analysis: For the power analysis for the primary analyses, we calculated the minimum detectable effect size (MDES) assuming $n = 200$, $\alpha = .05$, and power = .80 with a conservative estimate of 12 covariates in our model (see section 4.3). Power was calculated in R (R Core Team, 2018) using the pwr library (Champely, 2018). A power analysis was performed to quantify the MDES (measured as f^2) for a three-way interaction between the social buffering condition, sex, and pubertal stage within a multiple regression model controlling for all potential covariates, two-way interactions, and main effects (the most complex model considered in our primary analysis, see equation 1 below). Assuming these conditions, we should be able to detect an f^2 of 0.056. In other words, adding the three-way interaction to a model containing the covariates and all lower order interactions and main effects, the three-way interaction would need to explain an additional 5.6% of the variability to be detected. This falls between Cohen’s criteria for a small ($f^2 = .02$) and medium-sized effect ($f^2 = .15$) (Cohen, 1988). With a sample size of 200, even if we lost 40 of the participants, assuming all the previous conditions except a sample size of 160, we would still be power enough to detect an f^2 of .070, or still within a small-medium effect size. As the number of covariates decreases, the size of the MDES will decrease. Therefore, this represents a conservative estimate of power for our primary analyses as we are likely to have fewer covariates in our models and will use multiple imputation to correct for missing data. For the two-way interaction and main effects models, described below, the power will be larger than these reported values as the

PROTOCOL TITLE: Does Social Buffering Continue to be Effective Over the Peripubertal Period
When Friends Share the Stressor Experience?

VERSION DATE: v.3.3 3.31.23

models will be simpler. In addition, we ran a power analysis that corrected for multiple comparisons using the conservative Bonferroni's adjustment. Because we expect to run 9 independent multiple regression models or fewer, we ran our models assuming an alpha of 0.05 / 9. Based on this reduced alpha, we expect to be able to detect an effect of .07.

14.3 Statistical Analysis: The primary analyses will consist of a series of multiple regression models. For each dependent variable, Cortisol AUCi, Alpha-Amylase AUCi, we will begin by testing the three-way interaction between social buffering condition, sex, and pubertal stage for all outcomes. If the three-way interaction is not significant, we will then examine all two-way interactions. If the two-way interactions are not significant, we will then examine main effects only models. If the three-way interaction is significant, we will not examine any other model.

14.4 Data Integrity: *Multiplicity of testing.* We will correct for multiple comparisons using the Benjamini-Hochberg (BH) correction. The BH method works by controlling the false discovery rate, and relative to the Bonferroni's correction is more powerful, while still adequately protecting against Type I errors (Williams et al., 1999).

Missing data. If there is missingness in any of the dependent or independent variables, multiple imputation will be used (Little & Rubin, 2014; Peng et al., 2006; Schafer & Graham, 2002). Variables related to the missingness and the variables missing data will be included in the missing data model. In the event that missingness is not at random (MNAR), we will investigate the use of models for non-ignorable missing data.

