4.2 Drug/Device Handling: NA

4.3 Biosafety: NA

4.4 Stem Cells: NA

5.0 Procedures Involved

PROTOCOL TITLE: Does Social Buffering Continue to be Effective Over the Peripubertal Period
When Friends Share the Stressor Experience?

VERSION DATE: v.3.3 3.31.23

5.1 Study Design: **Rationale:** Adolescents experience social evaluation stress frequently. However, it is likely that often they are not alone, but with friends who are also going through the same experience. Thus, it is possible that under these conditions, social buffering by friends does not wane over the peripubertal period. Participants will be assigned to social conditions while engaging in an evaluative stressor task.

All sessions will occur ONLINE in a modification to accommodate COVID-19.

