There are four conditions in this experiment: Close Friend Who Also Completes the TSST, Close Friend Provides Social Support, Unfamiliar Peer Who Also Completes the TSST, and No Partner. The Close Friends and Unfamiliar Peer will complete the Network of Relationships Questionnaire and similar surveys about their relationship with the Target youth (Close Friend Conditions) or their own same sex best friend (Unfamiliar Peer). Both Close Friends and Unfamiliar Peer who complete the TSST will undergo the same procedures as the Target Child during session 2,

PROTOCOL TITLE: Does Social Buffering Continue to be Effective Over the Peripubertal Period
When Friends Share the Stressor Experience?

VERSION DATE: v.3.3 3.31.23

including salivary measures. Thus, we will have 50 boys and 50 girls who undergo the same procedures in parallel with the Target youth. We will have an additional 25 boys and 25 girls who provide social support but do not go through the same procedures.

5.2 Study Procedures:

200 target children, 11- 14 years of age will be tested in one of four conditions: 1) Close Friends Both Tested, 2) Unfamiliar Peers Both Tested, 3) Close Friend Gives Support, and 4) No Social Support.

Social Buffering Manipulations: Will include 4 between-subjects conditions and both sexes. Participants will be randomly assigned to Close Friend-Both Tested, Unfamiliar Peer-Both Tested, Received Support from Close Friend, and No Social Partner conditions. Definition of Close Friend. We will ask the parent to have the child select the close same-sex friend they want to have accompany them online. The parent then has to contact that child's family and get their permission for us to contact them. We have successfully conducted studies in which the child brings their best friend.

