Stressor Paradigm: TSST paradigm with the child facing a camera and two judges (one male, one female). After consent, parents are invited to exit the call (or leave the room); in our recent experience with a Zoom'd TSST, youth and parents readily agreed to this separation. A period of 'rest' begins where youth watch approximately 20-25 minutes of a mildly amusing child appropriate animated movie. The experimenter then sends them to a breakout room to begin the TSST sequence. They are greeted by 2 "judges", given instructions for the speech and told that they have 5 min to prepare. During that time, the judges turn off their audio/video but clearly remain in the breakout room. When 5 minutes elapse, the judges reappear. If the condition is one of support, the Peer or Friend is sent back to the main room and either released from the call or told to continue preparation for another 10 minutes until it is their turn. The judges give final speech instructions, and tell the youth to begin their speech, and then transition to the math. That participant is then excused back to the main room. If the condition calls for a Peer or Friend to perform the TSST, they are then sent to the judging breakout room and deliver their speech/math. After each participant completes the speech/math, they return to the main room and are greeted by the friendly experimenter, who guides them through REDCap links to the various surveys. At several points in session 2, saliva samples are obtained.

Note: In all conditions, one participant will be the target, even though in two of the conditions (Close Friends and Unfamiliar Peer Both Tested), both youth will go through the TSST and all physiological measures will be obtained. The reason for this is two-fold: (1) when we recruit we will know

PROTOCOL TITLE: Does Social Buffering Continue to be Effective Over the Peripubertal Period
When Friends Share the Stressor Experience?

VERSION DATE: v.3.3 3.31.23

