which youth is the target and this is the youth we select to balance pubertal stage and age, while in the close friend conditions, the close friend only needs to be within two years the age of the target youth; (2) in the “Close Friend Gives Support” condition, the friend will not be assessed and will only be there for moral support and to provide information on his/her friendship with the target youth. The collected data from the non-target youth will be analyzed using non-sponsored funds available to the PIs and co-regulation analyses may be conducted.

Note: These sessions will be recorded, as part of the challenge, to document the session, and to make behavioral response to the task available for later coding.

Pubertal Development: All youth will also complete the Morris and Udry (1980) pubertal development questionnaire, which allows placement in Tanner stages for hair, testicles, and breast development. **Questionnaires.**

Demographic Questionnaire: Parents will complete information on pre-tax family income, education level of parent(s), composition of the household, and medications that the child regularly takes.

Daily Diary: The parent and the youth both will report the following for the child that day: the time of wake up, estimated duration of sleep, medication usage, illness/fever, physical activity, and caffeine consumption.

Relationship Quality: Participants will complete the Network of Relationships Inventory - Behavioral Systems Version (NRI-BSV, Furman & Buhrmester, 2009) for the parent who accompanies them and their close friend. This questionnaire is based on an integration of attachment and Sullivanian theory and assesses three systems that are expected to be key in close relationships: attachment, caregiving and affiliation. The scales are: companionship, seek safe haven, seek secure base, provide safe haven, provide secure base, conflict, antagonism and criticism. We will also add 3 scales from the NRI-Relationship Qualities Version: Emotional Support, Approval and Satisfaction. Each scale consists of 3 items scored on a 5-point Likert scale. Psychometric qualities are high. Condition differences in quality of relationships will be examined and included as covariates if groups differ significantly. Otherwise, in follow-up analyses we will examine whether social buffering effects are stronger in relationships the child views as more supportive.

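### The covariate screen in 14.1 treats association with the randomised condition as a reason to adjust and sets no timing limit, so it can distort the condition effect if any candidate is affected by assignment

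*Combined protocol and SAP*

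**What the plan says.** Section 14.1 describes the purpose of the covariate data as finding "variables that are correlated with both the independent variable (social buffering condition, sex, pubertal stage) and the primary outcome measures". It then states: "Those covariates that are associated with the independent and outcome variables will be controlled for in the primary analyses". Its stated aim is unbiased estimates. It gives no rule on when a candidate must have been measured.

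Candidates are confined to a list "in section 4.3, Outcome Variables), we will conduct correlations or t-tests with pubertal stage". In this document the entry under that number reads "4.3 Biosafety: NA". Section 14.2 counts 12 covariates but does not name them.

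Section 5.2 adds its own triggers. For relationship quality: "Condition differences in quality of relationships will be examined and included as covariates if groups differ significantly". No association with the outcome is required. The health and behaviour scales enter if they differ by condition, pubertal stage or sex. Medication classes enter without a test.

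On timing, 5.1 places the target's relationship questionnaire and the health and behaviour questionnaire in Session 1, about two weeks before the stressor. Other data come later or depend on condition:
- The diary: "The parent and the youth both will report the following for the child that day".
- After the stressor task, participants are sent on to further questionnaires: "they return to the main room and are greeted by the friendly experimenter, who guides them through REDCap links to the various surveys".
- Under 5.1, partners rate their relationship with the target in the friend conditions, but their own best friend in the unfamiliar-peer condition.

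Section 14.1 randomises within sex-by-puberty strata. No section says whether this happens before or after Session 1.

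**The concern.** Screening covariates against an exposure makes sense when the exposure was not randomised. Here condition is randomised, so a variable fixed beforehand can be associated with it only by chance. The variables that the screen picks up systematically are those that assignment altered. If such a variable also relates to cortisol or alpha-amylase, adjusting for it takes its pathway out of the estimate. The effect of having a partner present is the trial's question, so the rule acts on the central contrast.

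Relationship quality is the named covariate for which this could happen. On the friend who attends, 5.2 says: "We will ask the parent to have the child select the close same-sex friend they want to have accompany them online". If the family already knows the condition when the child rates a friend, which friend is rated, and how, could depend on the condition. If partner reports are used, the person rated differs by condition by design, and the no-partner condition has no such report. Section 5.2 does not say whose report, or which session, supplies the covariate.

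**Working it through.** **Is there a figure to reproduce?** No. The plan attaches no number to the effect of covariate selection. The detectable effect in 14.2 concerns the three-way interaction and does not bear on this point.

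**Could assignment precede the ratings?** The strata need only sex and pubertal stage. Section 8.3 obtains an initial pubertal category from parents at recruitment, so randomisation before Session 1 is possible. In the friend conditions, 5.2 and 11.1 have the family approach the friend's family, and consent is sought before the online session. Those families therefore know the condition before Session 2. A diary completed on the Session 2 day would come after disclosure for them. This shows that the order is open, not that any rating was affected.

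**Formula.** Let T be the true total effect of one condition against the other three, a the shift that this condition causes in the covariate, and b the covariate's slope on the outcome. The adjusted estimate has expectation T − a·b. Worked cases with T = −0.60 SD (lower stress response):
- a = −0.8, b = 0.4: −0.60 + 0.32 = −0.28.
- a = −0.3, b = 0.2: −0.60 + 0.06 = −0.54.
- a = +0.5, b = 0.4 (opposite direction): −0.60 − 0.20 = −0.80.

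**Simulation of the 14.1 rule.** From the plan: 200 targets, 50 per condition. Assumed: T, a and b as shown; covariate with unit variance within condition; outcome variance within condition of 1. The covariate is adjusted for only if the ANOVA by condition and the correlation with the outcome both give p < .05. At least 6,000 runs per row. Effects are shown as magnitudes in SD.

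| Covariate | Shift | Slope | Selected | If always adjusted | Average under the rule |
|---|---|---|---|---|---|
| Fixed before assignment | 0 | 0.2 to 0.4 | 4% to 5% | 0.60 | 0.60 |
| Same direction | 0.3 | 0.2 | 28% | 0.54 | 0.57 |
| Same direction | 0.3 | 0.4 | 30% | 0.48 | 0.54 |
| Same direction | 0.5 | 0.2 | 69% | 0.50 | 0.52 |
| Same direction | 0.5 | 0.4 | 72% | 0.40 | 0.43 |
| Same direction | 0.8 | 0.4 | 99% | 0.28 | 0.28 |
| Opposite direction | 0.5 | 0.4 | 72% | 0.80 | 0.76 |

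The first row is the main result: for variables fixed before assignment, the screen fires at about the chance rate and leaves the average estimate unchanged. The other rows show what happens if a candidate is affected.

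**Which test is touched?** Section 14.3 tests the three-way interaction first, then the two-way interactions, then main effects. If condition shifts the covariate equally across sex and pubertal stage, the covariate carries no interaction component, and the interaction coefficients change by b × 0 = 0 in expectation. The calculation therefore concerns the condition main effect, which is the last step.

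**The case against.** The strongest reply is that the documents do not show the harm happening. A reader might infer from 14.1 that any variable can enter, that the rule does select consequences of assignment, and that it pulls the result towards no buffering. None of these is supported.

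- Candidates are limited to a list. The list is absent here, so nobody can say that it holds post-assignment variables.
- The two questionnaires named as covariates are placed in Session 1 for the target. The diary's sleep and caffeine items and the post-task surveys are not named as covariates. Self-rated stress, the most obvious mediator, is labelled a manipulation check.
- The direction is not fixed. Section 2.3 predicts that a friend who only gives support will raise stress responding. Adjusting for a stress-lowering variable that the friend's presence increased would enlarge that effect.
- The sizes rest on assumed values, and no effect on the first-step interaction test is shown.
- Sex and pubertal stage are not randomised, so screening against them is defensible.
- Sessions without consent for the friend are converted to the alone condition (11.1, 19.5). If these were analysed as received, pre-assignment variables could truly differ by condition.

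All of this stands, and it limits the point to a risk that the plan leaves open. It does not justify screening against a randomised factor. No passage excludes post-assignment variables, and Session 1 timing settles nothing while the timing of randomisation is unstated. If conversions cause imbalance, pre-assignment covariates named in advance can address it without this screen.

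**Conclusion.** The point holds as a fault in the selection rule. For condition, the screen gives no reduction in bias when candidates are fixed before assignment, and it preferentially picks any candidate that assignment has changed. The resulting distortion can go either way. Over the assumed range, a 0.60 SD effect averages between about 0.28 and 0.57 SD for a same-direction covariate, and rises to about 0.76 SD in the opposite-direction case shown. It is unchanged if no candidate is affected. These figures illustrate the mechanism and do not predict this trial's result. It would go too far to say that the plan will remove part of the buffering effect: no clearly post-assignment variable is named as a covariate. What the documents support is that nothing in them prevents it.

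**What to change.** 1. In 14.1, delete social buffering condition from the variables that covariates are screened against. Sex and pubertal stage can stay.
2. Replace the reference to the absent list with the covariates themselves, chosen in advance for their expected relation to cortisol and alpha-amylase.
3. Add wording such as: Primary models may include only covariates measured before assignment, or that assignment cannot affect.
4. State when randomisation occurs, and when families learn the condition, relative to Session 1.
5. In 5.2, remove the difference-by-condition trigger for relationship quality and for the health and behaviour scales. State whose report and which session supply relationship quality.
6. Use post-task surveys, partner reports and ratings of a friend chosen because of the assigned condition only in sensitivity or mediation analyses.

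The cost is a wording change and no new data. A covariate that happens to be imbalanced can no longer be added after the fact, and some same-day items, such as sleep or caffeine, may move to a sensitivity analysis.

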During Session 1, which will occur using the HIPAA-compliant version of Zoom the full consent & assent process will take place with parent & youth completing forms via REDCap. All youth who complete the TSST will have a full Session 1, while families whose youth merely attend as support will be given the study description by email or phone, and will be sent a link to REDCap for signing consent/assent. Parents will supply background information on family income, education and composition. Parents and the youth will complete the MacArthur Health and Behavior Questionnaire items for the Internalizing, Externalizing and ADHD scales, and reports of pubertal development. Youth will complete the Network of Relationships Questionnaire and other similar surveys in which they respond to questions about their relationships with their parents, their friend, and peers in general. Session 2 occurs approximately 2 weeks after Session 1. If the youth is in the one of the close friend conditions, their same sex close friend will also accompany them online. If they are in the unfamiliar peer condition, an unfamiliar peer of the same age and sex will be recruited and arrive online for session 2, likely with their parent. The TSST involves developing and delivering a speech and doing mental arithmetic while being judged/evaluated by two judges while being filmed over HIPAA-compliant Zoom. We will collect saliva for cortisol and alpha amylase assessment. Breakout rooms will be used in Zoom to create the different environments described below. For example, the session will start with a friendly experimenter who guides people through the online session, and participants will be sent to breakout rooms to either wait their turn or engage in the TSST task, and return to the main room with the friendly experimenter. We have successfully used this procedure in a recent study nearly identical to this one, with the exception of the Peer conditions.

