MacArthur Health and Behavior Questionnaire (HBQ) for 9-18 Year-Olds (Parent and Child, 2.1): This questionnaire was developed by Marilyn Essex based on the original HBQ for 4-8 year olds. We have used it many times. The scales we proposed to use here have high reliabilities (Cronbach

PROTOCOL TITLE: Does Social Buffering Continue to be Effective Over the Peripubertal Period
When Friends Share the Stressor Experience?

VERSION DATE: v.3.3 3.31.23

alpha's > .8). We will use the peer scales (acceptance/rejection, bullied, relational victimization, asocial, behavioral inhibition) and broad-band symptoms scales (Internalizing, Externalizing). These measures will be examined for balance across groups and if differences by condition, pubertal stage, or sex are found, will be entered as covariates.

Self-Report of Stress: As a manipulation check, participants will rate their arousal and emotional state at various points during each study using Likert-type scales

Version 2.0 addition: Added Child-self-report RSQ for Peer, Family, & Academic Stress, and PALS Student report of adaptation to challenge in environment.

Physiological Measures.

Stress Hormones: We will assay saliva samples for stress sensitive hormones: **cortisol** and **alpha-amylase**. Saliva will be collected using SalivaBio Oral Swabs (SOS) or passive drool and stored frozen at -30°C until shipped for assay. All testing will be conducted in the late afternoon to control for circadian rhythm. Medications will be recorded from parent report and classes of drug codes will be used to group meds by presumed mechanisms of action and will be entered as covariates (Granger et al., 2009). Systemic glucocorticoid medications are an exclusion criterion. For each analyte, we will calculate area under the curve from intercept (AUCi) to provide a single measure for the main analysis.

- 5.3 Study Duration: Participants will attend two sessions. Session 1 will be 1-1.5hr; Session 2 will be 2-2.5 hrs. It is expected that it will take approximately 2 years to enroll all study participants, and that the study will end, including data analyses, approximately 5 years after enrollment begins.

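### Sections 5.2 and 14.1 give different covariate-entry rules for the same primary models, so the covariate set is chosen after the data are seen; the cost is modest precision, not bias in the condition effect

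*Combined protocol and SAP*

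**What the plan says.** Four entry rules apply to the multiple regression models of section 14.3.

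- **Section 14.1, Preliminary Analyses** (each potential covariate): "Those covariates that are associated with the independent and outcome variables will be controlled for in the primary analyses". The others only describe the sample. The screening is specified as "we will conduct correlations or t-tests with pubertal stage, and t-tests, ANOVAs, or chi-square tests (as appropriate) with sex and condition".
- **Section 5.2, Relationship Quality**: "Condition differences in quality of relationships will be examined and included as covariates if groups differ significantly".
- **Section 5.2, HBQ**: the scales, "if differences by condition, pubertal stage, or sex are found, will be entered as covariates".
- **Section 5.2, Stress Hormones** (medication): "classes of drug codes will be used to group meds by presumed mechanisms of action and will be entered as covariates".

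Section 14.1 refers to section 4.3 for the candidate covariates. Section 14.2 does the same, computing power "with a conservative estimate of 12 covariates in our model (see section 4.3"). In this document that section reads "4.3 Biosafety: NA". Section 14.2 also expects that fewer than 12 covariates will be used in the end.

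**The concern.** A primary model should be fixed before the outcome data are examined. Here the covariates depend on significance tests run on the trial data, and the section followed decides which tests count. An HBQ scale that differs by sex but is unrelated to cortisol enters under 5.2 and stays out under 14.1. Because 14.1 requires a link to the outcome, the cortisol and alpha-amylase models could also carry different covariates; the plan does not say whether that is intended.

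The second issue is what 14.1 selects on. In a linear model with randomised conditions, a covariate earns its place mainly by predicting the outcome. Section 14.1 makes entry conditional on imbalance across condition, sex or puberty as well. A strong predictor that happens to be balanced is left out, and the precision it offered is lost.

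**Working it through.** **1. The rules side by side**

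| Covariate | Section | Difference on a design factor needed? | Outcome association needed? | Threshold given? |
|---|---|---|---|---|
| Relationship quality | 5.2 | Yes, condition | No | Significance, level not given |
| HBQ scales | 5.2 | Yes, condition, puberty or sex | No | No |
| Medication classes | 5.2 | No | No | Not applicable |
| Each potential covariate | 14.1 | Yes, condition, sex or puberty | Yes, but no test listed | No |

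No sentence ranks these rules.

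**2. The plan's own figure**

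Inputs from 14.2: N = 200, alpha .05, power .80, 12 covariates. The three-way term has u = 3 df (4 conditions, sex, continuous puberty). With 15 design terms, v = 200 − 12 − 15 − 1 = 172. A noncentral F test with λ = f² × N gives a detectable f² of .0558, and .0702 at N = 160 (v = 132). These match the stated .056 and .070. This point does not dispute them. That formula barely responds to the number of covariates, so it is not used for cost in step 6.

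**3. How often 14.1 drops a useful covariate**

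Assumptions: every screen at .05; the covariate is unrelated to condition, sex and puberty. The chance of passing at least one of three design-factor screens is 1 − .95³ = 14.3%, so at least 85.7% of such covariates fail. Adding the outcome screen by simulation (N = 200, 4,000 runs or more per value) gives the retention column below.

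**4. What that costs the lead test**

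Inputs: f² = .056, u = 3, λ = f² × N, v = 184 unadjusted and 183 with one covariate. Adjustment changes λ to f² × N / (1 − R²), where R² is the covariate's share of outcome variance (assumed). Unadjusted power is 80.2%. Power under the rule = kept × adjusted + (1 − kept) × unadjusted. At R² = .10: .137 × 84.6 + .863 × 80.2 = 80.8%.

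| Assumed R² | Kept by 14.1 | Power, rule | Power, always adjusted | Difference (points) |
|---|---|---|---|---|
| .02 | 7.6% | 80.3% | 81.1% | 0.8 |
| .05 | 12.6% | 80.5% | 82.4% | 1.9 |
| .10 | 13.7% | 80.8% | 84.6% | 3.8 |
| .20 | 14.6% | 81.5% | 88.9% | 7.4 |
| .30 | 14.5% | 82.1% | 92.9% | 10.8 |

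With λ = f²(u + v + 1) the levels fall by about 2 to 3 points, but the differences are similar (78.1% against 81.9% at R² = .10). These figures use alpha .05 and ignore the Benjamini-Hochberg step in 14.4.

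A covariate truly related to puberty fares differently. At R² = .10 it is kept 61% of the time when its correlation with puberty is .15, and 99% when it is .3.

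**5. Does the choice of rule change the result?**

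The HBQ rule in 5.2 and the 14.1 rule were simulated on the seven HBQ scales named in 5.2. Assumptions: scale intercorrelation .5, .05 screens, 1,000 runs per setting. With no true association the selected sets differed in 53% of trials; over five settings (scale-puberty correlation 0 to .3, scale-outcome correlation 0 to .2) the range was 13 to 94%. The p < .05 decision on the three-way test differed in only 0.1 to 2.9%. Type I error was 4.8 to 5.7%.

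**6. Cost of always adjusting**

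In simulation, covariates that predict nothing cut lead-test power from 80.4% to 79.0% (5 covariates), 78.6% (7) and 77.7% (12). With λ = f²(u + v + 1) the detectable f² is .0592 with none, .0609 with 5 and .0634 with 12. Five covariates repay their degrees of freedom once their joint R² exceeds about 1 − .0592/.0609, or 2.7% before rounding; twelve need about 6.5%.

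**7. Sex and puberty**

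These are not randomised. If an HBQ scale with R² = .10 confounds puberty and is omitted, the puberty slope shifts by r√R²: .15 × √.10 = .047, or .3 × √.10 = .095 SD per SD. If the scale lies on the pathway from puberty to the outcome, the same quantity is part of the effect.

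**The case against.** The best defence is that 14.1 is the governing statistical section and that 5.2 only describes measures, so the 5.2 rules form a first step before the 14.1 filter. One sentence could say so. The plan does not, and the 5.2 wording on HBQ scales and medication states that they will be entered, with no further condition. Even on that reading, 14.1 still lacks an outcome test and a threshold, and still selects on imbalance.

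The defence is right on several other matters.

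- A reader might infer that the screening biases the condition effect or inflates type I error. It does neither: conditions are randomised, and simulated type I error stays near 5%.
- A reader might take the 53% or 94% figures to mean that conclusions change that often. They count any difference between selected sets, and the lead decision rarely changes.
- A reader might infer that no candidate list was ever drawn up. Both 14.1 and 14.2 point to one, and 14.2 counts 12 covariates. What can be shown is a broken cross-reference. Likewise, 5.1 says "Parents and the youth will complete the MacArthur Health and Behavior Questionnaire items for the Internalizing, Externalizing and ADHD scales" while 5.2 names five peer scales with Internalizing and Externalizing; 5.1 lists what is completed and does not define a second candidate list.
- The precision loss rests on an R² that the documents do not give. Late-afternoon testing and untested entry of medication classes already limit some of the variance at issue. Whether wake time or sleep would be dropped cannot be told from the documents.
- Always adjusting is not free if the covariates turn out to be weak (step 6).

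**Conclusion.** The point stands as a SHOULD. The entry rules conflict, no order of precedence is stated, the 14.1 rule is incomplete, and the cited list is absent from the section named. The covariate set in every primary model is therefore settled after the data are seen. Of these, the conflict, the missing test and threshold, and the cross-reference rest on the text alone.

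The size is modest. Under .05 screens, a predictor unrelated to the design factors is dropped about 86 to 92% of the time. That costs about 1 to 4 points of power for R² of .02 to .10, and about 10 points only for R² near .30. Both the screen level and R² are assumptions. The documents do not support a claim that the condition comparison is invalid or that the lead result would often change.

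**What to change.** In 14.1, replace the significance screens, and the separate entry rules in 5.2, with one short covariate list written out in 14.1 itself, within the 12 allowed in 14.2.

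- Choose it on expected association with cortisol and alpha-amylase from data already collected, for example time since waking, sleep duration and medication class.
- Enter it in every primary model whatever the balance tables show, and keep those tables for description.
- Put possible confounders of sex and puberty, for example age and HBQ scales, in a pre-specified sensitivity model. State that adjusting for them changes what the puberty effect means and may remove part of it if they lie on the pathway.
- Say where relationship quality goes: only the follow-up moderator analysis already described in 5.2, or the sensitivity model.
- Correct the references to section 4.3, and give one HBQ scale list in 5.1 and 5.2.

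The cost is SAP wording and a few degrees of freedom, with no new data. If the chosen covariates predict nothing, power falls by about 1.5 points with 5 of them and 2.5 to 3 with 12, which is a reason to keep the list short.
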